Respirometry of platelets, peripheral blood mononuclear cells, and neutrophils on admission, 3 hours, 6 hours, 12 hours, 24 hours, 48 hours, and 5 days post admission; Development of multiorgan failure within 30 days of admission; Level of free serum free nucleic acids; Expression of pro and anti-inflammatory proteins and genes and genetic variants in serum, platelets, and white blood cells.

Background

Traumatic injury results in 5-6 million deaths per year worldwide with \$518 billion global cost with about half of trauma deaths due to acute blood loss. Acute blood loss and standard resuscitation with crystalloids and stored blood products causes hypothermia, acidosis, tissue hypoxia, hypotension, inflammation, the activation and consumption of coagulation factors including platelets, the release of free nucleic acids, the development of mitochondrial dysfunction and eventually organ failure. Importantly, about a quarter of trauma patients display a coagulopathy, (trauma induced coagulopathy, TIC) which greatly increases the risk of death and/or the development of multiorgan failure. We currently, however, cannot predict who will develop TIC or its associated complications. In fact, two patients who have the same clinical presentation may have very different outcomes. Developing a multi scale computational model and ex-vivo point of care assays would allow us to efficiently identify and effectively treat at risk patients and potentially improve outcomes.

Study Design

Phase*

Not applicable

Design

Prospective, observational, convenience sampling of trauma patients 18 yrs old or older who present to the trauma bay will be included. Minimally injured patients will be compared to those with a systolic blood pressure of 90 mmHg or less, the need for blood product transfusion within 1 hour of admission, and/or an ISS of greater than or equal to 15. Demographic data including past medical/medication history as well as clinical data including continuous vital signs (when available) will be recorded. Blood samples (approximately 15 ml) and urine samples (approximately 10 ml) will be taken on admission, 3hr, 6hrs, 12hrs, 24 hrs, 48 hrs, and 5 days post admission. Residual blood samples (which would otherwise be discarded) will be obtained from the PPMC clinical laboratory on 0 and 2 days post admission. Blood samples may be analyzed for coagulation parameters included ex vivo microfluidic

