48 hours and 5 days post admission. Blood and urine sample collection in unstable patients will be deferred or delayed if it is determined by the clinical team that taking the sample would interfere with clinical care. Smaller blood and urine volume samples maybe taken at each time point (eg 10 ml rather than 15 ml of blood) if research expertise is not available for sample analysis (e.g microfluidic or high resolution respirometry) at that time point. Residual plasma and whole blood samples will be collected from the PPMC clinical laboratory on day 0 and day 2 from trauma bay admission. Blood samples will be analyzed for coagulation and microfluidic flow parameters, proteins involved in inflammation and coagulation, mitochondrial function and respiration of white blood cells and platelets, DNA sequencing of specific genes involved in organ failure, and gene expression of proteins of interest. Residual samples will be further studied for protein biomarker measurements and DNA analyses. Urine samples will be analyzed for biomarkers of organ injury and dysfunction. Vital signs, number of blood transfusions, volume of crystalloid, administration of medications, and the values of routine laboratories will be monitored continuously for 24 hours, and then cumulatively for up to 5 days. This data will be collected by reviewing the electronic medical record via EPIC. Discrete data will be recorded on case report forms and then entered into REDCap - an institutionally approved and managed secure network that is also password protected. Continuous data will be deidentified and maintained on REDCap. The development of multiorgan failure will be monitored for up to 30 days post enrollment. If patients are discharged or die prior to completing the 5 days of blood samples, additional samples and/or clinic appointments for the purpose of research will not be obtained. After the last blood draw, we will be following the patient's outcome until discharge. This data is routinely extracted as part of the Pennsylvania Trauma Outcomes Study - a state trauma center requirement - and will not require additional contact with the patient. We will not personally follow up patients if they are discharged prior to 30 days.

The following documents are currently attached to this item:

There are no documents attached for this item.

Deception

Does your project use deception?

No

Analysis Plan

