This research involves minimal risk. The initial blood sample (15 ml) will be drawn at the time other blood samples are taken for standard clinical care. As such, it does not require an additional venipuncture. In total, 7 blood samples (a max of 15 ml per sample) will be taken over the course of 5 days. When research expertise is not available for specific assays (e.g microfluidics or respirometry) this blood volume will be decreased to 10 ml. Additionally, collections of research samples will be deferred or delayed if the clinical team feels that collection would interfere with the clinical care of an unstable patient. Moreover, a volume of 15 ml X 7 times over 5 days is the maximum amount of blood that will be collected. Many of these patients will be bleeding and will require a number of blood transfusions because of their injuries. Each blood transfusion is 300 ml. We do not feel that a maximum of 105 ml of blood over 5 days will pose a higher risk to our patients. Residual blood collection (which would otherwise be discarded) involves obtaining samples from the clinical lab on day 0 and day 2 and does not confer risk above loss of confidentiality. Lastly, sample collection of 10 ml of urine totaling 70 ml over 5 days imposes only minimal risk to the patient as it is a prospective collection via noninvasive means. The urine specimen will be obtained at the time staff is performing a clinical draw and collected directly from a Foley catheter or, if a catheter is not in place as part of standard care, from a spontaneous void.

Impact on Subject Rights and Welfare*

This study will attempt to protect the patient's rights by (1) informing and consenting the patient or surrogate prior to the initial blood draw and urine collection whenever practicable (2) informing and obtaining consent for continued participation when a surrogate is identified and (3) informing and consenting the patient when he/she regains capacity to make an informed choice. If consent is not obtained, the subject will be un-enrolled and the data and biological samples will be discarded.

Waiver Essential to Research*

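### After admission, platelet respirometry (and platelet expression, if measured then) may partly measure donor platelets, and the analysis plan has no step that separates donor product from patient biology

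*Combined protocol and SAP*

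**What the plan says.** All places are in the combined protocol and SAP.

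- **Secondary outcome variable(s).** The first item listed is "Respirometry of platelets, peripheral blood mononuclear cells, and neutrophils on admission, 3 hours, 6 hours, 12 hours, 24 hours, 48 hours", with a last sample at day 5. The list also has "Expression of pro and anti-inflammatory proteins and genes and genetic variants in serum, platelets, and white blood cells", for which no time points are given.
- **Design.** "Minimally injured patients will be compared to those with a systolic blood pressure of 90 mmHg or less", or with "the need for blood product transfusion within 1 hour of admission, and/or an ISS of greater than or equal to 15". This is a single comparator group with three alternative entry routes.
- **Minimal Risk.** "Many of these patients will be bleeding and will require a number of blood transfusions because of their injuries". No transfusion rate is given.
- **Waiver Essential to Research.** Severely injured patients often receive blood products within minutes of arrival. The same section says that data and samples need to be obtained ahead of interventions.
- **Procedures.** The number of transfusions is collected from the electronic record. Product type, and timing relative to each research draw, are not listed. Draws in unstable patients may be put off. "Residual plasma and whole blood samples will be collected from the PPMC clinical laboratory on day 0 and day 2", and these residual samples are used for protein biomarkers and DNA analyses.
- **Analysis Plan.** T-tests or Mann-Whitney tests compare patients who develop coagulopathy, altered cellular respiration or multi-organ failure. Logistic regression looks for risk factors, with no covariates listed. Transfusion is not mentioned.

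**The concern.** Transfusion differs here from an ordinary confounder. If a patient has received platelets or whole blood before a draw, some of the platelets in the tube may belong to someone else. The assay result is then a mixture of patient and donor cells, whatever the patient's own mitochondria are doing.

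Exposure to that mixture is tied to the planned comparisons. A patient who needs transfusion within 1 hour falls on the severe side by definition. Patients who develop coagulopathy or organ failure may also have been transfused more often. One of the Analysis Plan's groups, altered cellular respiration, is itself defined by this kind of assay, so a patient's group could depend partly on donor cells.

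At stake is interpretation. The Background names stored products as well as blood loss among the causes of mitochondrial dysfunction. A later difference in platelet respiration could reflect injury, an effect of transfusion on the patient's cells, or donor platelets in the sample. The plan has no analysis that tells these apart.

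**Working it through.** **No figure to reproduce.** The target of 300 subjects comes with no alpha, power, effect size or SD, and the documents give no transfusion rate, product mix or donor fraction. What follows is an illustration of size.

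**Inputs from the documents**
- 300 subjects (Subjects enrolled by Penn Researchers).
- Roughly 30% of trauma alerts turn out not to have significant injury (Key inclusion criteria). This gives 0.30 × 300 = 90 minimally injured and 300 − 90 = 210 others.

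**Assumptions**
- All 210 others meet a severity criterion, and every sample is assayed.
- s = share of the severe group given a platelet-containing product before the draw, 0.1 to 0.5.
- f = donor fraction of the platelets assayed in those recipients, 0.1 to 0.5.
- d = donor-to-patient difference, 0.5 to 1.0 SD.
- No recipients among the minimally injured, within-group SD of 1, and no true difference in patient biology.

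**Formulas**
- Spurious shift: δ = s × f × d.
- SE = √(1/90 + 1/210) = √(0.01111 + 0.00476) = 0.126 SD.
- Two-sided 5% rejection rate: Φ(δ/SE − 1.96) + Φ(−δ/SE − 1.96).

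| s | f | d | δ (SD) | δ/SE | Rejection rate |
|---|---|---|---|---|---|
| 0.1 | 0.1 | 0.5 | 0.005 | 0.04 | 5.0% |
| 0.5 | 0.1 | 1.0 | 0.05 | 0.40 | 6.8% |
| 0.3 | 0.3 | 1.0 | 0.09 | 0.71 | 11% |
| 0.5 | 0.3 | 1.0 | 0.15 | 1.19 | 22% |
| 0.5 | 0.5 | 1.0 | 0.25 | 1.98 | 51% |

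These rates are per time point, against a nominal 5%. The top row of the range needs half of the severe group to have received a platelet-containing product and half of their assayed platelets to be donor platelets. If only 30% were recipients, the same average donor share of 25% would need f = 0.25/0.30 = 83%.

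**Fewer assays.** The Accrual section says that not every patient will have every assay at every time. If one third of subjects are assayed (30 versus 70, an assumption), SE = √(1/30 + 1/70) = 0.218 SD. Shifts of 0.05 to 0.25 SD then give about 6% to 21%.

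**The case against.** The other side has a good deal to say.

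- **The severe group is not a transfused group.** A reader might infer that one arm of the comparison is defined by transfusion. It is not: low blood pressure or an injury severity score of 15 or more is enough for entry, so the group can include patients never transfused. The documents also give no transfusion rate for the minimally injured. This stands.
- **Contamination is conditional.** The documents refer only to blood products. Donor platelets reach the assay only if a platelet-containing product was given. This stands, and it is why the point says may. The respirometry outcome also covers mononuclear cells and neutrophils, and the documents give no basis for extending the point to them.
- **The tests named are by outcome, not by severity.** The Design section states the severity comparison, but the Analysis Plan attaches no test to it. This stands, but the outcome-based contrasts are open to the same mixing.
- **Transfusion is not ignored, and the aim is prediction.** Counts are recorded, an admission sample is planned, and for pure prediction the state of circulating blood may be useful whatever its origin. This stands in part. It does not help where a later difference is read as the patient's own mitochondrial dysfunction, and the Analysis Plan gives the admission sample no priority.
- **The size is assumed throughout.** This stands.

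**Conclusion.** The gap is real but modest. Platelet respirometry is planned at six times after admission, transfusion can precede all of them, and nothing in the plan separates donor from patient platelets. Later contrasts by severity or by outcome can therefore carry a donor component. For platelet expression the point applies only if it is measured after admission, which the documents leave open.

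The size cannot be settled from the documents. The range of about 5% to about 51% per time point rests wholly on the assumed donor share, donor-to-patient difference and group sizes. It should not be read as an estimate of the trial's error rate. The lower end is negligible.

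A reader might go further and conclude that the later platelet results are invalid, or that the severity comparison is in effect transfused versus untransfused. The documents support neither: product type is not stated, and transfusion is only one of three routes into the group. No sample-size figure and no primary outcome changes. This is a cheap improvement to secondary analyses.

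**What to change.** 1. **Lead time point.** Make the admission sample the lead time point for platelet respirometry and expression contrasts, where it was drawn before any transfusion. Flag admission samples that were not. The documents do not address transfusion before arrival or in transferred patients, and draws in unstable patients may be delayed.
2. **Data.** Extract product type and time relative to each research draw from the electronic record, which is already being reviewed. The transfusion count alone is not enough.
3. **Later time points.** Report each contrast overall and again in samples with no prior platelet-containing product, with the second labelled a sensitivity analysis.
4. **Adjustment.** Treat any model that adjusts for units given as exploratory. Transfusion also marks severity and may lie on the causal path, so adjustment can remove a real injury effect.
5. **Genotyping.** State that DNA comes from the admission research draw where possible. Use residual day-0 or day-2 blood only when it precedes transfusion or the patient was untransfused. A day-0 residual sample is not guaranteed to be pre-transfusion.

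The cost is a few sentences in the Analysis Plan and a small extra data extraction. The downside is that the restricted subset will be smaller and less severely injured, so it can support the overall contrast but not replace it.

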Clinical trials identifier: **NCT03128658**

Principal Investigator: **[name]**

Protocol Title: **Trauma Induced Coagulopathy and Inflammation**

Date: **August 2, 2018**

Protocol Description: **This is a prospective observational trial designed to evaluate the factors that contribute to the development of trauma induced coagulopathy, post injury inflammation and the development of organ dysfunction in adult trauma patients. Demographic data, physiologic data, blood samples and clinical variables will be collected over the 5 days following traumatic injury.**

Protocol

Abstract

While a number of factors are known to be associated with the development of trauma induced coagulopathy (TIC), inflammation, and multi-organ failure, we currently cannot predict which patients are at risk for developing these life-threatening conditions with any certainty. In this prospective observational study, we will investigate the many factors that contribute to the development of trauma induced coagulopathy, post injury inflammation and the development of organ dysfunction in order to develop a multi scale computational algorithm and ex vivo models capable of clinical prediction. Using a convenience sample technique, demographic data, physiologic data, fresh and residual blood samples, urine samples, and clinical variables will be collected over 5 days following traumatic injury. In addition to a computational model, ex vivo models using microfluidic devices and high resolution cellular respirometry, and nucleic acid analysis will be used to predict the development of TIC and multi-organ failure.

Objectives

Overall objectives

1) Develop a computational algorithm to predict the development of trauma induced coagulopathy (TIC) 2) Validate ex-vivo microfluidic TIC models 3) Develop ex-vivo assays to predict the development of trauma-induced inflammation and the development of multi-organ failure

Primary outcome variable(s)

Coagulation parameters including thromboelastography and microfluidic assessment on admission, 3 hours, 6 hours, 12 hours, 24 hours, 48 hours, and 5 days post admission.

Secondary outcome variable(s)

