This will be prospective observational study using convenience enrollment. Injured patients who present to the trauma bay will be evaluated by the on call trauma surgeon and as well as the PARC research assistant. If eligibility criteria are met, the research blood samples will be drawn at the same time as routine clinical samples. Depending on the research expertise available (e.g. microfluidic assessments or cellular respiration experiments), eligible patients may not have all the research variables investigated at each time point. Given that we will be recruiting a number of minimally injured patients, as well as injured patients with significant variability (eg severity of injury, age, gender, race, and past medical history), a large accrual number is required in order to develop a computational model that can accurately determine which factors predict the development of TIC, inflammation and

multiorgan failure.

Key inclusion criteria

In order to develop a robust predictive model, we will need to include a variety of injured patients ranging from minimally injured to severely injured. Inclusion criteria, therefore, will include any trauma alert activation. This highest level of activation is reserved for patients who meet either physiologic parameters (e.g. hypotension) or who have a mechanism of injury that would suggest significant injury (e.g. high speed motor vehicle crash). that being said roughly 30% of trauma alerts are not found to have significant injury. Only patient's whose age is equal to or greater than 18 years old will be included.

Key exclusion criteria

Transfer to trauma service of greater than 6 hours Known pregnancy - these patients are excluded because drawing multiple blood samples has an unknown risk to the fetus. Women of child bearing age, however, will be eligible. If they are found to be pregnant before enrollment, they will be excluded (eg. obvious gravid uterus, + fetus seen on trauma ultrasound, or + pregnancy test, which is routinely done on all female trauma patients) . If they are found to be pregnant after the initial blood draw, this sample will be processed, but no additional blood samples will be taken. The patient, or next of kin if appropriate, will be asked to consent for analysis of the processed sample and for continued clinical data collection.

Vulnerable

Populations

Children Form

Pregnant women (if the study procedures may affect the condition of the pregnant woman or fetus) Form

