Patients who develop coagulopathy, altered cellular respiration, or multi-organ failure will be compared using T-tests or Mann-Whitney tests for continuous variables and Chi-squared or Fischers exact tests for dichotomous variables. Spearman's rank correlation will be used to assess associations between continuous variables. Logistic regression analysis will be used to identify risk factors for the development of trauma induced coagulopathy or multiorgan failure.. Receiver operating characteristic curves will be used to assess accuracy of microfluidic measurements compared to standard measures of coagulation . Continuous deidentified data including vital signs, laboratory values, and medications will be shared with collaborators at Princeton University in order to create a mathematical model. The computational whole-patient systems model is a multiscale, multi-compartment model whose state-space is defined by a very large and heterogeneous set of variables as well as a large number of input parameters. It is straightforward to make direct contact with the clinical trauma blood profiles because the measured variables in these profiles are also included in the model state space. This comparison first will be used to establish the validity of the model. Here, the model will simply be integrated in time for various initial trauma conditions in an attempt to determine whether the model can be predictive. In particular, we will determine whether it is possible to reproduce the variation between the various time states at admission,3, 6, 12, 24, 48 hours and 5 days post admission. A more challenging data mining application is to discover new variables that are more predictive of clinical outcomes than those employed in current clinical protocols. The workhorse data mining technique we plan to explore, extend, and use to establish links between our multiscale model and clinical data is known as Diffusion Maps. This is a framework based upon diffusion processes for finding meaningful geometric descriptions of data sets, even when the underlying geometry of the data is complex, nonlinear and corrupted by noise. The method is based on the construction of a Markov transition probability matrix corresponding to a random walk on a graph whose vertices are the data points with transition probabilities being the local similarities between pairs of data points. The framework relates the spectral properties of Markov processes to their geometric counterparts and it unifies ideas arising in a variety of contexts such as nonlinear dimensionality reduction methods, machine learning, and harmonic analysis. The first few eigenvectors of the sparse Markov matrix are then used to generate a new set of intelligent coordinates that embody the intrinsic geometry of the data set. These are the diffusion map coordinates. Most importantly, these eigenvectors integrate the local similarities into a globally efficient low-dimensional representation of the complex geometric structure. The usage of eigenvectors of similarity matrices for dimensionality reduction is not new. In fact, the classical method of principal component analysis (PCA) computes principal components as eigenvectors of the covariance matrix of the data set and find a low dimensional representation of the data by projecting it onto the subspace spanned by the first few principal components that capture the most variability (or energy) of the data. Diffusion Maps is a successful generalization of PCA to complex nonlinear data sets whose structure is unknown in advance: unlike PCA, the diffusion map coordinates are nonlinear projections of the data; moreover, the nonlinear embedding is based only upon local similarities of neighboring data points. Diffusion Maps first will be used on the multiscale simulation data sets. This will establish macroscopic observables that define the trajectory of the overall patient-scale model. This is crucial because it is much simpler to establish a connection to patient outcome when only a few variables are being tracked (instead of the large variable space that defines the full multiscale model). However, these variables are generally not obviously connected to clinical variables and we will use the simulation data to establish relationships between the Diffusion Maps variables and actual measureable quantities. The result of this work will be to isolate variables that are highly predictive of patient outcome and allow assessment of different interventions.

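### For Objective 3's inflammation target, the conventional analyses are unadjusted and ignore the admission level, so an ex-vivo assay that only tracks existing inflammation can look predictive

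*Combined protocol and SAP*

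**What the plan says.** Overall objectives, item 3, reads: "Develop ex-vivo assays to predict the development of trauma-induced inflammation and the development of multi-organ failure". Inflammation appears among the secondary outcomes only as "Expression of pro and anti-inflammatory proteins and genes and genetic variants in serum, platelets, and white blood cells". No marker, threshold or time point turns that into an endpoint.

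The Analysis Plan lists these conventional methods:

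- **Group tests:** "Patients who develop coagulopathy, altered cellular respiration, or multi-organ failure will be compared using T-tests or Mann-Whitney tests for continuous variables", with chi-squared or Fisher's exact tests for dichotomous variables. Inflammation does not define a group. It can enter only as a variable compared between groups.
- **Spearman's** "rank correlation will be used to assess associations between continuous variables". No pairs, time order or adjusted version are given.
- **Regression:** "Logistic regression analysis will be used to identify risk factors for the development of trauma induced coagulopathy or multiorgan failure". Inflammation is not among the outcomes and no covariates are listed.
- **ROC curves:** "Receiver operating characteristic curves will be used to assess accuracy of microfluidic measurements compared to standard measures of coagulation".

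Separately, the Accrual section justifies the sample size by the need for "a computational model that can accurately determine which factors predict the development of TIC, inflammation and" multiorgan failure. The Analysis Plan describes this model as follows: "the model will simply be integrated in time for various initial trauma conditions". It is then compared with the measured states from admission to day 5.

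Under Design, blood is scheduled at admission, 3, 6, 12, 24 and 48 hours, and 5 days, so an admission level is available by design.

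**The concern.** Many inflammatory markers are continuous, are sampled serially here, and may already be raised in the first sample. If an assay reflects the admission level and that level persists, the assay will correlate with later levels even when it adds nothing to knowing the admission value. An unadjusted correlation or group comparison cannot separate this persistence from prediction.

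At stake is the inflammation half of Objective 3. The study could report that an assay predicts the development of inflammation when it has only detected inflammation already there.

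**Working it through.** **No plan figure to reproduce.** Planned enrolment is 300, with no stated alpha, power or effect size. The question is how often the unadjusted methods would flag an assay with no added information.

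**Inputs from the plan.** N=300 is a ceiling, because Accrual says not every research variable will be measured at every time point. Smaller N matters too, since Data and Safety Monitoring schedules an analysis after every 50 subjects.

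**Assumed inputs.** The correlation of assay with admission marker is a, that of admission with later marker is b, and each is taken from 0.3 to 0.7. Testing is two-sided at 0.05. Marker and assay are normal on the analysis scale. The Mann-Whitney test compares the top quarter of assay values with the rest, standing in for a group such as altered respiration.

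**Model.** Assay and later marker each depend only on the admission marker, so the assay adds nothing once that is known. The expected crude correlation is then a × b, for example 0.5 × 0.5 = 0.25.

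**Simulation (2,000 studies per setting), share declared significant:**

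| N | a / b | a × b | Spearman, unadjusted | Mann-Whitney | Spearman, partial on admission level |
|---|---|---|---|---|---|
| 300 | 0.3 / 0.3 | 0.09 | 31.8% | 19.9% | 5.5% |
| 300 | 0.5 / 0.5 | 0.25 | 98.6% | 88.8% | 5.6% |
| 300 | 0.7 / 0.7 | 0.49 | 100% | 100% | 6.3% |
| 100 | 0.5 / 0.5 | 0.25 | 66.3% | 41.9% | 5.2% |
| 50 | 0.5 / 0.5 | 0.25 | 36.0% | 21.4% | 5.2% |
| 50 | 0.3 / 0.3 | 0.09 | 9.6% | 7.3% | 5.1% |

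Over all 16 settings run, the partial correlation was significant in 4.3% to 7.6% of studies.

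**Analytic check.** The Spearman value is (6/π) × asin(ab/2), which is 0.239 for ab = 0.25 and 0.086 for ab = 0.09. With Fisher's z:

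- N=300, 0.5/0.5: atanh(0.239) × √297 = 0.244 × 17.23 = 4.21; Φ(4.21 − 1.96) ≈ 98.8%.
- N=300, 0.3/0.3: 0.0862 × 17.23 = 1.485; Φ(1.485 − 1.96) ≈ 31.8%.
- N=50, 0.5/0.5: 0.244 × √47 = 1.67; Φ(1.67 − 1.96) ≈ 39%, against 36.0% simulated.

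**Does adjustment also gain precision?** Take a = 0.5 and b = 0.6. The crude residual variance is 1 − 0.30² = 0.91. The adjusted residual variance is 1 − 0.36 = 0.64, but only 1 − 0.25 = 0.75 of the assay's variance remains. The variance ratio for the assay coefficient is 0.91 / (0.64/0.75) = 1.07, which is not material.

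**The case against.** **The computational model.** A reader might infer that unadjusted methods are the only route to inflammation anywhere in the plan. The documents do not support that. Accrual gives the computational model this task as well, and the Analysis Plan starts that model from the patient's initial state and places the measured blood-profile variables in its state space. This objection stands against an unqualified claim. It does not close the gap for the assays. Objective 1 assigns the algorithm to TIC, and Objective 3 assigns inflammation to the ex-vivo assays. The data described as shared for modelling are vital signs, laboratory values and medications. Nothing says that inflammation is a model output or that an assay will be evaluated through the model.

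**Marginal prediction may be enough.** The plan does not explicitly ask for value beyond the admission marker, and an assay that correlates 0.25 with a later level does predict it marginally. That is fair for description. But the objective concerns the development of inflammation, and a crude association cannot distinguish that from inflammation already present.

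**Change from admission is not excluded**, since no Spearman pairs are named. It is not specified either, and a crude change score has its own baseline dependence. With a = b = 0.5 and equal variances, an uninformative assay correlates (0.25 − 0.50) / √(2 × (1 − 0.5)) = −0.25 with change.

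**Adjustment makes real value harder to show.** Suppose the standardised coefficient is 0.15 beyond baseline, with correlations of 0.5 (assay-baseline) and 0.6 (baseline-later). The crude r is 0.15 + 0.5 × (0.6 − 0.15 × 0.5) = 0.41. The partial r is (0.4125 − 0.30) / (√0.75 × √0.64) = 0.16. This is correct. It is the price of answering the incremental question.

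**Conclusion.** The concern holds in a limited form. Among the conventional methods, Objective 3's inflammation target is reached only by unadjusted Spearman correlation or crude comparisons. None defines an inflammation endpoint, orders assay before outcome, or uses the admission level.

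An assay with no information beyond that level can then look predictive: in about 32% to 100% of studies at N=300 over the assumed correlations, and about 36% at N=50 with 0.5/0.5, against about 5-6% after adjustment.

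Two stronger conclusions are tempting but unsupported:

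- **That such an assay will look predictive.** The documents give neither the correlations nor the number of complete pairs. With 0.3/0.3 at N=50 the rate is only 9.6%.
- **That adjustment is worth 1/(1 − 0.36) = 1.56 times the sample size.** That figure requires an assay uncorrelated with the admission marker. At an assay-baseline correlation of 0.5 the factor is about 1.07.

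The case for change is interpretability, not power. The rates also rest on the two-sided 0.05 level, normality, and the top-quarter split for the group test.

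**What to change.** In the Analysis Plan:

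1. Name the inflammatory marker or markers and one later scheduled time point. Twenty-four hours is one example; the choice should be justified.
2. For each ex-vivo assay, regress the log marker level at that time on the admission assay value, with the log admission level of the same marker as covariate. ISS may be added if justified.
3. Report the adjusted coefficient and the partial R-squared, with confidence intervals.
4. Keep Spearman correlation as description. Base any claim that an assay predicts inflammation beyond what is already present on the adjusted result.
5. If the computational model is also meant to evaluate the assays, say how.

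**Cost.** This is analysis wording only, since the samples are already scheduled. Patients lacking either sample drop out of the model. Under Procedures, collection may be deferred or delayed in unstable patients and stops at death or discharge, so these losses are unlikely to be random. The number and characteristics of those lost should be reported. Adjustment also removes only what the named marker measures, so that choice should be made before the data are examined.
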